Title:	The Impact of Two Medtronic Infusion Sets (a 3-day Set & a 7-day Set) on Lipohypertrophy (LH) in Persons with Type 1 Diabetes (T1D) and Thought to Have LH
Protocol Number:	1.0
Date of Protocol:	June 9, 2021
Unique Protocol ID (NCT ID not yet assigned)	299_CELazio1_220322

Synopsis

Title	The impact of two Medtronic infusion sets (a 3-day set & a 7-day set) on lipohypertrophy (LH) in persons with Type 1 diabetes (T1D) and thought to have LH.
Study Number	ERP-2021-xxxx
Devices	
Investigational devices: None
 
Non-Investigational devices:
 
 Medtronic Extended Wear Infusion Set (EWIS) (MMT- 433 & MMT-443) Medtronic Quick-set™ Infusion Set (MMT-396 & MMT-398) MiniMed™ 670G Insulin Pump (MMT-1781) Guardian™ Sensor (3) (MMT-7020) Guardian™ Link (3) Transmitter/Recorder Guardian™ Link Charger Tester CareLink™ USB CareLink™ Clinical Therapy Management Bayer Contour ® Next (or Plus) Link 2.4 Meter Bayer Contour ® Next (or Plus) Test Strips Bayer MICROLET®2 Lancing Device (usage is optional) Bayer MICROLET® Lancets (usage is optional) Precision Xtra™* ketone meter or equivalent ketone meter MiniMed™ 3-day Reservoirs (MMT-332A/MMT-326A) MiniMed™ 7-day Reservoirs (MMT-342) AA batteries (Lithium or Alkaline) Insulin Pump accessories, including activity guard, skins kit, belt clip.
Purpose/Objective	
The purpose of this study is to assess the impact of two Medtronic infusion sets (a 3-day set & a 7-day set) on lipohypertrophy (LH) in persons with Type 1 diabetes and thought to have LH.
 
This is an observational study using ultrasound (US) and palpation to assess the impact of infusion sets on lipohypertrophy (LH) in an infusion set crossover study.

What is Lipo-hypertrophy?	
Lipohypertrophy (LH) occurs in subcutaneous tissue as a result of the lipogenic effect of repeated insulin exposure. The fat cells enlarge and proliferate resulting in thickened tissue, sometimes forming lumps under the skin. LH is associated with suboptimal glycemic control.

	
This is a 1-center, prospective, open label, 2-arm study of ≥ 16 subjects who use the insulin pumps. These subjects will be using 2 types of infusion sets for two periods of 3 months each type that will serve as an exploratory pilot study to assess the impact of infusion sets on LH (see Figure 1 for study design).

Study Design	
Figure 1. Study Design
 
Each subject will use their own MiniMed™ 670G insulin system as usual. Each subject will be given 2 types of infusion sets to wear and change sets per label use (3 days for Quick-set™ and 7 days for EWIS). Each type of infusion set with the longest length (43" in) will be used for this study. 7-day reservoirs will be used with the Medtronic Extended and 3-day reservoirs will be used with the Quick-set™. The infusion set(s) or reservoir(s) can be replaced independent of each other for Medtronic Extended.
 
The subject will use either Medtronic Extended or Quick-set™ infusion set for consecutive 3 months. During the three-month period, either the right side or the left side of the abdomen will be designated for one or the other infusion set (defined randomly). For each type of infusion set, a coordinate rule for site rotation will be given to have the Set placed in a specified area (left or right side) of anterior abdominal wall (see appendix).
 
For each placement/wear, a daily log will be given to the subject to record time and location for the infusion set placement. Patients will be instructed to recognize areas of clinical apparent LH sites and refrain from inserting in these areas. At home, the subject will be expected to inspect their infusion site on a daily basis and if they observe signs of infection (i.e. erythema > 1 cm in diameter with warmth, pain, and/or induration) at the infusion site, they should call the investigational center. In addition to the study procedures, the subjects are to continue their standard routine care. In the end of each month, the subject should self-inspected by palpation for LH and record the findings on the daily log.
 
At each study visit, insulin pump and CONTOUR® NEXT LINK 2.4 study meter will be uploaded into CareLink™ Personal For Clinical Research. Also, all the infusion sites will be examined ultrasonically for LH.

	
At each visit the clinical team will assess the skin in a systematic using the palpation method procedure and the US evaluation procedure (see appendix).
 
All participants will be asked to give demographic details and medical history. They will be asked to complete a series of questionnaires about their pump routine, diabetes distress, insulin treatment satisfaction and quality of life. All participants will have a baseline glycated hemoglobin (HbA1C) taken. The Total Daily Dose (TDD) will be calculated based on the CareLink™ data.

Sample Size and Investigational Center	
The study will be conducted at up to 1 investigational center. It is anticipated that approximately 16 subjects will complete the study.
 
Up to 20 subjects may be screened.
 
As this is an exploratory study - no power assumptions are planned.

Study Duration	The study is anticipated to last up to 12 months.
Inclusion Criteria	
Subjects will be considered for enrollment in the study if they meet all of the following criteria:
 
 1. Clinical diagnosis of type 1 diabetes and has been a pump user for at least 10 years 2. Using a MiniMed™ 670G or 640G Insulin pump with Guardian sensor 3. Age 18 to 80 years 4. Hemoglobin A1c level less than or equal to 10% 5. Not currently known to be pregnant, nor planning pregnancy during the study. 6. Willingness to follow the protocol and sign the informed consent 7. Use U100 Humalog (insulin lispro) or U100 NovoRapid/Novolog (insulin aspart)
Exclusion Criteria	
Subjects who meet any of the following criteria are not eligible for study participation and these exclusion criteria are study specific:
 
 1. Conditions that affect the skin evaluation, e.g. scleroderma or amyloidosis 2. A known medical condition that in the judgment of the investigator might interfere with the completion of the protocol. 3. Pregnant or lactating females 4. Subject has Glycosylated hemoglobin (HbA1c) > 10 % at time of screening.
LH Detection by Palpation and Ultrasound	LH identification by palpation and Ultrasound will follow literature method, as described in Gentile et al. SpringerPlus (2016) 5:563; A suitable palpation technique allows to identify skin lipohypertrophic lesions in insulin-treated people with diabetes

	
Enrolled subjects will have 5 investigational site visits.
 
Visit 1: Informed Consent and Screening.
 
Visit 2: Initial LH examination by ultrasound. Device training and Set 1 distribution (13 Medtronic Extended or 30 Quick-set™ infusion sets). A coordinate rule for site rotation will be given to have the Set 1 placed in a specified area (left side or right side) of anterior abdominal wall.
 
Visit 3: LH examination by ultrasound & Set 2 distribution (13 Medtronic Extended or 30 Quick-set™ infusion sets, different from Visit 1). A coordinate rule for site rotation will be given to have the Set 2 placed in opposite site of anterior abdominal wall used for Set 1.
 
Visit 4: End of study- 90 ± 7 days
 
Visit 5: 6-month examination
 
  
 Data Collection	VISIT 1*	VISIT 2*	VISIT 3*	VISIT 4* End of Study	Visit 5* Post-Study	
   
 Visit number	1	2	3	5	6	
 
 Informed consent	X					
 
 Enrollment screening	X					
 
 Demographics	X					
 
 Medical history	X					
 
 Local HbA1c	X			X	X	
 
 CareLink Clinical upload		X	X	X	X	
 
 Infusion set training		X	X			
 
 Diary collect and review			X	X	X	
 
 Collection of study sets			X	X		
 
 Ultrasound examination		X	X	X	X	
 
 Pain/comfort/Infusion set questionnaire				X	X	
 
 Adverse events and device deficiencies				X	X	
 
 Study deviations				X		
 
 *Unscheduled visit may be arranged upon patient observation of site reaction.	
  
	Data Collection	VISIT 1*	VISIT 2*	VISIT 3*	VISIT 4* End of Study	Visit 5* Post-Study	Visit number	1	2	3	5	6	Informed consent	X					Enrollment screening	X					Demographics	X					Medical history	X					Local HbA1c	X			X	X	CareLink Clinical upload		X	X	X	X	Infusion set training		X	X			Diary collect and review			X	X	X	Collection of study sets			X	X		Ultrasound examination		X	X	X	X	Pain/comfort/Infusion set questionnaire				X	X	Adverse events and device deficiencies				X	X	Study deviations				X		*Unscheduled visit may be arranged upon patient observation of site reaction.					
Data Collection	VISIT 1*	VISIT 2*	VISIT 3*	VISIT 4* End of Study	Visit 5* Post-Study																																																																																												
Visit number	1	2	3	5	6																																																																																												
Informed consent	X																																																																																																
Enrollment screening	X																																																																																																
Demographics	X																																																																																																
Medical history	X																																																																																																
Local HbA1c	X			X	X																																																																																												
CareLink Clinical upload		X	X	X	X																																																																																												
Infusion set training		X	X																																																																																														
Diary collect and review			X	X	X																																																																																												
Collection of study sets			X	X																																																																																													
Ultrasound examination		X	X	X	X																																																																																												
Pain/comfort/Infusion set questionnaire				X	X																																																																																												
Adverse events and device deficiencies				X	X																																																																																												
Study deviations				X																																																																																													
*Unscheduled visit may be arranged upon patient observation of site reaction.																																																																																																	

Subject Stopping Rules
	
 1. Retracting of Patients consent 2. Unanticipated Adverse Device Effects (UADEs); 3. Diabetic Ketoacidosis (DKA); 4. Severe hypoglycemia events that result in subject requiring paramedic assistance, an Emergency Room (ER) visit or subjects who experience seizure, coma or death. 																																																																																																

Statistical Analysis for Endpoints and Hypothesis	
Primary Endpoint
 
The primary endpoint is the event rate of lipohypertrophy (LH).
 
The study will be evaluated and summarized, including but not limited to the following:
 
 • Self-assessed LH by palpation using a visual analogue scale (VAS) 1 to 10, coupled with clinical examination by a physician if possible • LH (appearance, location, mass, indices of vascularization and distribution) characterized by ultrasound. Standardized semiquantitative description will be used: variations in the thickness of the subcutaneous adipose tissue; single/multiple mass; size/dimension measurement; vascularisation index, flow index and vascularisation flow index; dense, fibrotic; localized, diffused, etc. • The relationship between the observed LH and infusion set type, TDD, glycemic control, HbA1C etc. • Satisfaction of infusion sets using validated questionnaire, e.g. the diabetes treatment satisfaction questionnaire (DTSQ) 
Statistical analysis may be performed for relationship determination.
 
Exploratory Endpoints
 
 • Descriptive of site reactions. Pain at the infusion site device related issues (leakage, occlusion in fluid path, etc.). • Descriptive of set failure cases: accidental pull out, adhesive tape issues, infection, erythema and/or induration. • Descriptive of catheter explants: • Gross examination for cannula kinking and crimping. • Pain and comfort questionnaires. • Samples of infusion set, insulin, and sensors will be stored for future analysis including microscopy and chemistry. 
Descriptive Endpoints
 
A number of Descriptive Comparisons of Interest will be made. They include, but are not limited to, the following
 
 • Continuous Glucose Monitoring (CGM) data, Time Above Range (TAR): Duration, and Area Under the Curve (AUC) when Sensor Glucose >180, >240, and >250 mg/dL • CGM data, Time Below Range (TBR): Duration, AUC when Sensor Glucose <50, <60, and <70 mg/dL • CGM data, Time in Range (TIR): Duration, AUC when Sensor Glucose > 70 e < 180 mg/dL • Glycemic variability: Standard Deviation (SD), Coefficient of Variation (CV), Mean Amplitude Of Glycemic Excursions (MAGE) • Cohort analysis by age • Cohort analysis by duration of diabetes
--	---

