APPENDIX

Site rotation of infusion set

The infusion sets should be placed on the side of abdomen designed for each one type of set. The subject should choose areas with a reasonable fat pad rotating the infusion site in an organized fashion, using a 4 x 4 pattern starting from right lateral upper quadrant and going from right side to left side **and numbering from 1 to 16 for abdomen left side and from 20 to 29 for abdomen left side**. A site rotation tool kit of Association of Diabetes Care and Education Specialist will be provided to each patient(<https://www.diabeteseducator.org/docs/default-source/living-with-diabetes/tip-sheets/insulin-injections/siterotat toolkit.pdf>).

The subject should place the new infusion set about five cm from the previous one keeping the old infusion set on the body can serve as a good reference point for placing the new infusion set. The following areas must be avoided:

- A five cm area surrounding continuous glucose sensors
- Sites that have existing lipodystrophy
- A five cm area surrounding the navel, skin folds and scars
- Places subject to prolonged restrictive pressure from sitting, sleeping and tight clothing
- Sites that have very little subcutaneous fat tissue

Lipohypertrophy (LH) identification protocol

A validated protocol previously published [*Gentile S. et al. Diabetes Ther (2020) 11:2001–2017*], will be performed to LH identification. It consists of:

1. the inspection of each area of interest using direct and tangential light against a dark background.
2. a palpation technique involving slow circular and vertical fingertip movements followed by repeated horizontal attempts on the same spot. The pressure of the fingers on the skin must be initially gentle and then gradually increase. The pinch manoeuvre will be performed when perceiving a harder skin, to comparing the thickness of the suspected spot to that of surrounding areas. The abdominal examination will be performed with the patient lying supine and standing on afterward; for thigh examination, they will be asked to seat with the legs bent and the feet on the floor.

High-Frequency Skin Ultrasound Scans

High-frequency B-mode skin ultrasound scans (USS) will be performed at all infusion sites by experienced ultrasound scan (US) operator using the linear 15 MHz probe (EsaoteMyLab Alpha, Novarium SRL, Rapallo, Italy) with the patient in the supine position.

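### The daily log, as described, has no field for why or when a set came off, and device-deficiency questions skip the crossover visit, so causes of first-period set failures rest on recall of up to about 180 days

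*Protocol*

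**What the plan says.** **What the log holds.** The protocol synopsis, Study Design, states that "a daily log will be given to the subject to record time and location for the infusion set placement". It adds that at each month's end "the subject should self-inspected by palpation for LH and record the findings on the daily log". These are the only log entries the protocol names. Subjects are to look at the site every day, but are not told to write down what they see. Signs of infection call for a telephone call to the centre.

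**What is to be reported.** The Exploratory Endpoints include "Descriptive of set failure cases: accidental pull out, adhesive tape issues, infection, erythema and/or induration" and "Pain at the infusion site device related issues (leakage, occlusion in fluid path, etc", inspection of removed cannulas for kinks and crimps, and pain and comfort questionnaires.

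**When the clinic asks.** In the visit schedule, the diary is reviewed at Visits 3, 4 and 5 and used sets are collected at Visits 3 and 4. Adverse events with device deficiencies, and the pain/comfort/infusion set questionnaire, are marked at Visits 4 and 5 only. A footnote allows an unscheduled visit if the subject notices a site reaction.

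**How the sets are used.** Subjects "change sets per label use (3 days for Quick-set™ and 7 days for EWIS"), and "The subject will use either Medtronic Extended or Quick-set™ infusion set for consecutive 3 months". Visits 2 and 3 each hand out 13 Extended or 30 Quick-set sets.

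**The concern.** A set that is pulled out, peels, leaks or hurts leaves its cause in the subject's memory unless someone writes it down. The protocol lists these causes as things to describe for each set, but gives the log no place for them. It then skips the device-deficiency question at the one visit that separates the two sets.

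At stake is the descriptive comparison of tolerability and failure between a 3-day and a 7-day set. A cause first asked about after the crossover may be lost, or recalled but assigned to the set worn more recently. No later analysis can recover a cause that was never recorded, so the statistical analysis plan cannot repair this.

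**Working it through.** **1. Reproduce the protocol's set counts.** Inputs: a period of 90 days (three months; the visit list gives 90 ± 7 days for Visit 4) and labelled wear of 3 and 7 days.
- Quick-set: 90 / 3 = 30.
- Extended: 90 / 7 = 12.86, rounded up to 13.

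Both match the numbers handed out. The ratio is 30 / 13 = 2.3.

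**2. Planned placements in the study.** With about 16 completers: 16 × 30 = 480 Quick-set and 16 × 13 = 208 Extended. These are scheduled placements, not failures. The protocol gives no failure rate, so the number of events affected cannot be derived from it.

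**3. Time to the first scheduled question about a failure.** Assume that Visit 3 falls 90 days after Visit 2, and Visit 4 falls 90 days after Visit 3.
- First-period event, earliest: 90 + 90 = 180 days before Visit 4.
- First-period event, latest: 90 days before Visit 4.
- Second-period event: 0 to 90 days before Visit 4.

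If the ± 7 days applies to each period, the longest delay runs from 83 + 83 = 166 to 97 + 97 = 194 days. With the same question at Visit 3, the longest delay in either period would be about 90 days. The set worn first therefore always carries the longer recall.

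**4. Endpoint against source.**

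| Exploratory item | Source named in the protocol at the time of the event | Left to recall |
|---|---|---|
| Infection signs | Call to the centre | Little |
| Milder site reaction | Optional unscheduled visit | Anything not reported |
| Site pain | None of its own | Yes, to Visit 4 |
| Pull-out, adhesive problem, leakage | None for the cause | Yes, to Visit 4 |
| Occlusion | None named; pump upload might help, but no such use is stated | Yes, unless the upload is used |
| Kinked or crimped cannula | Returned set, Visits 3 and 4 | The finding no; no stated link to its placement |

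**5. Wear time.** Successive logged placement times give the interval between placements, and an interval shorter than the label flags an early change. This approximates wear but does not give the removal time: the Appendix notes that "keeping the old infusion set on the body can serve as a good reference point for placing the new infusion set", so the old set may come off after the new one goes in, and a gap without a set would not show either. For Extended, pump reservoir records are no substitute, because "The infusion set(s) or reservoir(s) can be replaced independent of each other for Medtronic Extended".

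**The case against.** The strongest reply is that the gap is narrower than it looks.

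- The log is not confined to time and place; it also takes the monthly palpation findings.
- Infection signs prompt a call, other site reactions may lead to an extra visit, and kinking is judged on the returned set itself.
- An early failure that leads to a new set does leave a dated log line. Only its cause is missing.
- The synopsis need not list every log column; a fuller form may exist elsewhere.
- The affected endpoints are exploratory and descriptive, in a pilot without power assumptions.

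All of this stands, and it limits the point. It does not remove it. The call covers infection signs only, and the extra visit is optional and tied to site reactions, so neither would capture a pull-out, a peeled adhesive or a leak. The diary review at Visit 3 cannot retrieve what the log has no field for. The protocol refers to no fuller form, and the schedule gap at Visit 3 exists whatever the log's layout.

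A reader might also infer that actual wear is unknown, so that LH at a position cannot be related to exposure. The documents do not support that: placement time and location are logged, so the interval at each position can be approximated. A set left on briefly as a landmark changes this little, if insulin delivery has moved to the new set (an inference).

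**Conclusion.** The point holds as a limited weakness in data capture. Followed as written, the protocol provides no record at the time of the event for why a set came off, or for site symptoms short of infection. It first asks about first-period device problems 90 to 180 days after they happen (up to 166-194 days at the extreme if the window applies to each period). By then the subject has worn the other set for about three months. The descriptions affected cover 480 and 208 planned placements in 16 subjects.

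This rests on two 90-day periods, on the diary in the schedule being the daily log, and on no fuller log form being in use.

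Two stronger conclusions do not follow. Nothing in the protocol shows that failures of one set would be under-reported more than those of the other; the 30 to 13 imbalance makes differential loss possible, but its direction is conjecture. Nor is the primary LH endpoint at risk, since LH is assessed by palpation and ultrasound and does not depend on failure reasons. The change is worth making because it is cheap, not because the study's main result hangs on it.

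**What to change.** 1. Add to each log line the removal date and time, the reason for removal (scheduled, pull-out, adhesive, leakage, occlusion, pain, skin reaction, other) and a 0-10 site-pain score at removal.
2. Have the subject write the log line number on the bag of each returned set, so that a kinked cannula can be traced to its placement.
3. Mark adverse-event and device-deficiency collection and the pain/comfort questionnaire at Visit 3 as well as at Visits 4 and 5.
4. State that the exploratory failure and explant endpoints are taken from the log line.

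Cost: extra log columns, a numbered bag, a few more seconds for the subject at each set change, and a few minutes at a visit that already takes place. No new visit or staff is needed, and no treatment rule changes. If a fuller log form already holds these fields, the protocol need only refer to it, and items 2 to 4 remain.

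### The self-palpation VAS for lipohypertrophy has no score before Set 1 and is not specified by side of the abdomen

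*Protocol*

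**What the plan says.** The first measure listed in the Protocol under Primary Endpoint is "Self-assessed LH by palpation using a visual analogue scale (VAS) 1 to 10, coupled with clinical examination by a physician if possible". Its timing comes from the Synopsis, Study Design: "In the end of each month, the subject should self-inspected by palpation for LH and record the findings on the daily log". The visit schedule has no row for self-palpation, and its row "Diary collect and review" is first marked at Visit 3, after Set 1 has been worn.

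On location, Study Design says "a daily log will be given to the subject to record time and location for the infusion set placement". That covers where the set is placed. Nothing there or under Primary Endpoint says that the LH score is given by side or by site.

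Side is nevertheless what separates the two sets. Study Design has it that "either the right side or the left side of the abdomen will be designated for one or the other infusion set (defined randomly"; the visit list adds for Visit 3 "A coordinate rule for site rotation will be given to have the Set 2 placed in opposite site of anterior abdominal wall used for Set", meaning the first set. No washout is stated. Subjects are described in the title as thought to have LH, and the inclusion criteria require that each "has been a pump user for at least 10 years", so some LH at entry is expected.

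The other LH measures are placed differently. Study Design has the clinical team palpate at every visit. Ultrasound is scheduled at Visits 2 to 5, and the Appendix compares fat thickness with time zero.

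**The concern.** The layout keeps the two sets apart on the body, so that what happens on one side can be read as the effect of one set. It can do that for the self-score only if the score is kept by side and has a value from before the set was worn. The protocol provides neither explicitly.

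Two things follow. First, Set 2 has the month-3 score as a starting value, while Set 1 has none. Second, if subjects give one number for the whole abdomen, the scores in months 4 to 6 also include whatever Set 1 LH can still be felt on the other side. Both are matters of data collection: no later analysis can create a score that was never taken or divide a single score between sides.

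**Working it through.** The protocol states no effect size, standard deviation, alpha or power, so there is no figure to reproduce. The check is a reading of the schedule followed by a simple additive model.

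**Schedule.** Each set is worn for 3 months, giving month-end self-scores at months 1, 2 and 3 for Set 1 and 4, 5 and 6 for Set 2.

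| Measure | Reading before Set 1 | Reading at the change to Set 2 |
|---|---|---|
| Self-palpation VAS | none scheduled | month 3 |
| Clinician palpation | Visits 1 and 2 | Visit 3 |
| Ultrasound | Visit 2 | Visit 3 |

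**Model for one abdominal score (all values assumed, in VAS points).** Let o be old LH, a the growth on set A, b the growth on set B, and c the share of Set 1 LH still felt at the end of Set 2, from 0 to 1. For a subject who takes A first:

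- month 3 = o + a
- month 6 = o + c·a + b
- A − B from these scores = (a − b) − c·a

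For a subject who takes B first, A − B = (a − b) + c·b. Averaging the two orders equally gives (a − b)(1 − c/2). Old LH drops out of all three expressions.

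With o = 3, a = 1 and b = 2, the month-3 score is 4 (A first) or 5 (B first). At c = 1 the month-6 score is 6 in either order: 3 + 1 + 2 or 3 + 2 + 1.

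| Assumed growth | True A − B | Set order | c = 0 | c = 0.5 | c = 1 |
|---|---|---|---|---|---|
| a = 1, b = 2 | −1 | balanced | −1.0 | −0.75 | −0.5 |
| a = 1, b = 2 | −1 | all A first | −1.0 | −1.5 | −2.0 |
| a = 2, b = 1 | +1 | balanced | +1.0 | +0.75 | +0.5 |
| a = 2, b = 1 | +1 | all A first | +1.0 | 0 | −1.0 |

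Changing o from 3 to 0 leaves every entry the same.

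**Would one of the two changes be enough?** Take A first.

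- A Visit 2 score, still one number for the abdomen: Set 1 change = (o + a) − o = a, which is right. Set 2 change = (o + c·a + b) − (o + a) = b − (1 − c)·a, which equals b only if c = 1. With a = 1 and b = 2 it reads 1, 1.5 and 2 at c = 0, 0.5 and 1.
- Scores by side, but none at Visit 2: Set 2 change on its own side is b for any c. Set 1 change still has no starting value.
- Both: Set 1 side, Visit 2 to month 3, gives a. Set 2 side, month 3 to month 6, gives b. Neither depends on c, provided old LH on that side is stable over the period.

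**The case against.** The self-score is one item in an open list under a primary endpoint defined as the LH event rate. The study is an exploratory pilot of about 16 subjects. Clinician palpation and ultrasound have readings before Set 1, and the ultrasound is done at the infusion sites. This stands, and it confines the point to the self-score. Those measures do not replace it, however: they are different measurements, no visit is scheduled at months 1, 2, 4 or 5, and the physician examination paired with the self-score is only to be done if possible.

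The absence of a split by side is silence, not a rule. The log form is not shown, its layout is often left to the diary, and the recorded findings could include location. This also stands. If the log already asks for side, the carry-over disappears and one sentence in the protocol would say so; the missing score before Set 1 would remain.

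A reader might go further and infer that old LH biases the comparison of sets, or that two equal sets would look different. The documents do not support either in general. Stable old LH sits in both sets' scores and cancels within subject. With equal growth, the balanced-order contrast is zero; a spurious difference needs unequal numbers in the two orders. The visit list allows either set type to come first, so both orders are foreseen. Yet the only mention of randomness in Study Design attaches most naturally to the side, and no ratio of orders is given, so balance cannot be taken for granted.

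**Conclusion.** The point holds, with limited reach. As scheduled, the self-palpation VAS has no value before Set 1, so Set 1 change from before wear cannot be computed; months 1 to 3 show only movement after wear has begun. That part rests on the schedule alone.

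The carry-over is conditional on two things that the protocol does not settle: that one abdominal score is used, and that some Set 1 LH persists. Given both, balanced order dilutes a true difference, by up to half at full persistence, and unbalanced order can bias it in either direction, including a change of sign in the assumed example. The sizes are illustrations; the protocol gives no persistence figure.

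It would be too strong to conclude that the self-scores tell nothing about either set. Month 3 is a usable start for Set 2, and if Set 1 LH persists fully, month 6 minus month 3 recovers Set 2 growth. Nor does the gap extend to the clinician or ultrasound measures. This is an inexpensive improvement to one listed measure, worth making before the first subject starts Set 1 because the missing score cannot be recovered afterwards.

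**What to change.** - Take one self-palpation VAS at Visit 2, before Set 1 is placed. Device training already happens at that visit.
- Record every self-score, at Visit 2 and at each month end, separately for the left and right abdomen.
- State that each set is credited with the change on its own side over its own wear period: Visit 2 to month 3 for Set 1, and month 3 to month 6 for Set 2.

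The cost is one more column on the daily log, one extra self-score, and slightly more burden for the subject. No added visit, staff or procedure is needed, and no sample size or power figure changes because none is stated.

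### Four promised questionnaire topics have no row in the visit schedule, so neither a pre-wear value nor an end-of-first-set value is secured

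*Protocol*

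**What the plan says.** The Study Design section of the synopsis says that all participants will complete "a series of questionnaires about their pump routine, diabetes distress, insulin treatment satisfaction and quality of life". The sentence before it reads "All participants will be asked to give demographic details and medical history", and the sentence after it reads "All participants will have a baseline glycated hemoglobin (HbA1C) taken". No visit is given for the questionnaires.

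The visit list names no questionnaire at any visit. Visit 1 is consent and screening. Visit 2 includes "Device training and Set 1 distribution (13 Medtronic Extended or 30 Quick-set™ infusion sets"), so wear begins from there. The change of set follows at "Visit 3: LH examination by ultrasound & Set 2 distribution".

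The data collection schedule is printed twice, and the two copies agree. The one questionnaire row is "Pain/comfort/Infusion set questionnaire", marked at Visits 4 and 5 and blank at Visits 1, 2 and 3.

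Under Statistical Analysis for Endpoints and Hypothesis, the items to be evaluated include "Satisfaction of infusion sets using validated questionnaire, e.g. the diabetes treatment satisfaction questionnaire (DTSQ"). No assessment time is attached to it.

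**The concern.** When an instrument is given is a matter for the protocol. A statistical analysis plan can settle scoring and models, but it cannot supply an answer that nobody was asked to give. Site staff work from the schedule, and here it omits four topics that the narrative promises.

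Two time points are at stake. One is before Set 1. From Visit 2 the study prescribes the set, the side of the abdomen and the rotation pattern, so a later question about current pump routine would describe the study's routine and not the subject's own. The other is Visit 3. A crossover earns its value from having each subject's response under both conditions. If satisfaction is first recorded after the second set, the response to the first set is not captured while that set is in use.

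**Working it through.** No power or sample-size figure bears on this point, so the check is a comparison of the narrative, the schedule, the visit list and the endpoint list.

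**Step 1. Where the items in the narrative paragraph fall in the schedule**

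| Item | V1 | V2 | V3 | V4 | V5 |
|---|---|---|---|---|---|
| Demographics | X | | | | |
| Medical history | X | | | | |
| HbA1c | X | | | X | X |
| Pump routine | no row | | | | |
| Diabetes distress | no row | | | | |
| Treatment satisfaction | no row | | | | |
| Quality of life | no row | | | | |
| Pain, comfort and infusion set form | | | | X | X |

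The three neighbouring items all have a mark at Visit 1, so the paragraph reads as a description of entry data. The four questionnaire topics standing between them have none. Topics with a row: 0 of 4.

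**Step 2. Questionnaire marks of any kind, by position in the crossover**

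- Before Set 1 (Visits 1 and 2): 0.
- End of the first set period (Visit 3): 0.
- End of the second set period (Visit 4): 1, the pain, comfort and infusion set form.
- Post-study (Visit 5): 1, the same form.

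Visit 4 is read as the end of the second set period because it is labelled the end of study, and because collection of used sets is marked at Visits 3 and 4 only.

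**Step 3. What this leaves for the satisfaction outcome**

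A within-subject comparison of the two sets needs one value per set: Set 1 at Visit 3 and Set 2 at Visit 4. Suppose the existing infusion set form is meant to carry satisfaction, which the protocol does not say. Then the schedule supplies 1 of these 2 values at the time of use. The other would have to be recalled at Visit 4, after a second set has been worn for a further period that the protocol sets at 3 months. The alternative is to compare Visit 4 answers between subjects who finished on different sets. That gives up the pairing in a study expecting about 16 completers.

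**The case against.** The strongest reply is that the missing row is a clerical gap. The table is plainly not exhaustive: the clinical team is to palpate at each visit, yet palpation has no row, and neither does handing out the sets. Its visit-number line also runs 1, 2, 3, 5, 6. The narrative places the questionnaires beside a baseline measurement, which suggests that completion at entry was intended. This largely stands, and it limits what can be claimed.

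A reader might infer that the baseline of these four questionnaires is lost. The documents do not support that. Nothing assigns them to Visit 4, and the narrative points towards entry. The supported statement is that no visit is secured. Nor does the late timing of the pain and comfort form measure any delay in these four: it is a different form, and questions about the study sets could not be asked before those sets are worn.

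A reader might also infer that change from the subject's usual set becomes impossible to state, or that an explanation for lipohypertrophy at entry is forfeited. The protocol plans no comparison with the usual set, and it does not name earlier site practice as a cause of lipohypertrophy. Earlier routine could also still be asked about later, though less reliably.

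The objection does not remove the gap at Visit 3. The narrative paragraph describes entry data, so even a generous reading of it puts no questionnaire at the end of the first set period. Satisfaction with the sets is nevertheless listed for evaluation.

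**Conclusion.** The point holds as an inconsistency between the narrative and the schedule, with a practical consequence for one listed outcome. None of the 4 promised topics has a row. No questionnaire is marked before wear, and none at the end of the first set period. Followed as written, the schedule does not allow satisfaction with the two sets to be compared within subject except by recall after the second set.

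This rests on two assumptions: that sites follow the schedule where it and the narrative differ, and that Visit 4 closes the second set period. If sites instead act on the narrative and collect all four topics at entry, the pre-wear part of the concern falls away and the Visit 3 part remains.

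The importance is low. The study is exploratory, the primary endpoint is the event rate of lipohypertrophy, and nothing here touches it. Scoring and analysis of the questionnaires may be set out in a statistical analysis plan and are not in question.

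**What to change.** Reconcile the Study Design text with the schedule by adding a row (or one row per instrument), marked as follows:

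- **Visit 2, before Set 1 is handed out:** pump routine, distress, treatment satisfaction and quality of life. The pump-routine form should ask about usual practice before the study.
- **Visit 3, about Set 1, and Visit 4, about Set 2:** at least treatment satisfaction.

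The text should also say which instrument carries the satisfaction outcome, since the endpoint list gives the DTSQ only as an example, and whether the existing infusion set form is meant to serve that purpose.

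The cost is small. If each topic was meant to be given once, the narrative already implies 4 topic administrations per subject. The proposal makes 4 + 1 + 1 = 6, so 2 more, all at visits already planned. The downside is a little added questionnaire time for subjects.
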